#### **1.4. Rationale for Dose**

In Phase 2 trials in RA, pooled data with an exposure response analysis demonstrated a dose-dependent increase in efficacy up to 200 mg total daily dose. In the Phase 2 study of CD, subjects treated in the 200 mg arm showed favorable response and remission rates (47% remission over 23% placebo and 59% response over 41% placebo). The remission rate at Week 20 for subjects who failed placebo for the first 10 weeks and commenced 100 mg from Weeks 10 to 20 was slightly lower (32%) though the response rate was comparable (59%), indicating some level of efficacy at the 100 mg dose. These results are consistent with the relationship observed between filgotinib exposures and inhibition of pSTAT1 activation (ex-vivo) following single and multiple filgotinib doses, where maximal inhibition of pSTAT1 activation (~78%) was achieved at or above 200 mg total daily dose and intermediate inhibition (~47%) at 100 mg {[Namour 2015](#)}. pSTAT1 data, in conjunction with considerations around the margin for nonclinical testicular findings, suggests assessing doses above 200 mg is not indicated. The presence of response in CD subjects in the exploratory 10 to 20 week arm of Study GLPG0634-CL-211, and study of multiple doses (ie, 100 mg and 200 mg once daily) in the present study will enable establishment of an appropriate nominal dose and determine the dose with the most favorable risk/benefit profile for SBCD subjects.

#### **1.5. Risk/Benefit Assessment for the Study**

Crohn's disease is a progressive and potentially life-threatening disease with few treatment options, many of which result in primary or secondary nonresponse. Inflammatory bowel disease may lead to increased risk of gastrointestinal malignancies, impairment in quality of life, and ultimate need for life-altering surgery. Current treatment options are limited in ability to establish mucosal healing and clinical remission and have significant safety and efficacy limitations; for example, biologics have significant immunogenic risks and steroids are associated with increased morbidity and mortality. Remission rates are generally low when compared to placebo rates across most therapies for IBD. There remains substantial unmet need in IBD, particularly in moderate to severe disease. The lifelong nature of IBD increases the probability that subjects have cycled through various therapies, leaving few approved options. SBCD diagnosis and therapy faces the unique challenge of difficulty imaging and tracking response to therapy, and represents a subset of CD with increased risk of complications such as penetrating disease.

Nonclinical studies in rats and dogs identified lymphoid tissues and testes as target organs for filgotinib in long-term repeat-dose toxicity studies. Although decreased lymphocyte numbers observed in nonclinical studies have not been seen in clinical studies, hematological assessment will be performed throughout the present study to ensure this potential risk is appropriately monitored. In both rats and dogs, microscopic findings in the testes included germ cell depletion and degeneration, with reduced sperm content and increased cell debris in the epididymis and reduction in fertility in male rats. The dog was determined to be the most sensitive species. When using the mean exposure AUC at the NOAELs for dogs in the 26-week and 39-week chronic toxicity studies, and the 39-week targeted exposure toxicity study, the exposure margins compared with the highest proposed clinical dose of 200 mg once daily are 2.5, 1.9, and 3.6-fold respectively, in subjects with CD. A male safety study is planned to examine the potential effect of filgotinib on sperm/ejaculate parameters. Pending those results, the use of 200 mg in males in

the United States will be limited to subjects who have failed at least 2 biologic therapies (any TNF $\alpha$  antagonists and vedolizumab). Refer to the IB for further information about nonclinical testicular findings.

Administration of filgotinib produces an increase in embryofetal malformations in pregnant rats and rabbits at exposures similar to, or slightly higher than, exposures associated with a 200 mg once daily dose in CD subjects; the use of highly effective contraception in the subject population is expected to mitigate this risk.

JAK inhibition is expected to increase the risk of infection based on mechanism of action. Across global studies with filgotinib, in general, active treatment arms have increased incidences of infection versus placebo. In the present protocol, treatment interruption and discontinuation considerations surrounding infections are incorporated and sites and investigators will be trained regarding such circumstances. All subjects will be screened for tuberculosis (TB) and subjects with active infections will be excluded. Malignancy has been reported in subjects on filgotinib; in the present trial, subjects will be required to have up to date colorectal cancer screening and surveillance and subjects with recent malignancies will be excluded as outlined in the eligibility criteria. For further details about infections and malignancies, please reference the IB.

The potential benefits of JAK inhibition include improvement in clinical symptoms and mucosal and endoscopic healing. JAK inhibition may be efficacious in the treatment of IBD based on results from FITZROY. A lack of response contingency after Week 10 will enable early access to active drug when clinically indicated. In FITZROY, an increase in mean hemoglobin concentration was observed, without difference between filgotinib and placebo. No clinically significant changes from baseline in mean neutrophil counts or liver function tests were observed at 10 weeks. Filgotinib treated subjects showed an increase in HDL and no significant change in LDL. Lipid and hemoglobin effects represent potential benefits in this population.

An independent data monitoring committee (DMC) appointed to monitor the study will provide an additional level of risk mitigation. The DMC may advise to continue the study unchanged, to modify the study, or to discontinue the study. The initial meeting will occur after approximately 20% of the planned total number of subjects reach the Week 10 visit. Following this, the next meeting will occur after approximately 50% of subjects reach the Week 10 visit. Additional DMC meetings may be convened, if needed.

Taking all of these considerations into account with respect to the filgotinib program, the early signals for efficacy demonstrated in the CD clinical trial, as well as the beneficial findings in nonclinical models of disease and the overall safety, tolerability, and PK characteristics of filgotinib that have been elucidated to date, there is a favorable benefit-risk profile for this agent in continued development as a treatment for SBCD. The overall risk/benefit balance of this study is considered favorable.

For additional information about the risks of filgotinib, reference is made to the filgotinib IB.

## **1.6. Compliance**

This study will be conducted in compliance with this protocol, Good Clinical Practices (GCP), and all applicable regulatory requirements.

## 2. OBJECTIVES

The primary objective of this study is:

- To evaluate the efficacy of filgotinib, when compared to placebo, in establishing clinical remission, defined as CDAI < 150, at Week 24

The secondary objectives of this study are:

- To evaluate the impact of filgotinib, when compared to placebo, on change in segmental MaRIA score for all assessed small bowel segments at Week 24
- To evaluate the efficacy of filgotinib, when compared to placebo, in establishing segment level MaRIA remission at Week 24
- To evaluate the efficacy of filgotinib, when compared to placebo, in establishing segment level MaRIA response at Week 24
- To evaluate the efficacy of filgotinib, when compared to placebo, in establishing subject level small bowel MaRIA remission at Week 24
- To evaluate the efficacy of filgotinib, when compared to placebo, in establishing subject level small bowel MaRIA response at Week 24
- To evaluate the efficacy of filgotinib, when compared to placebo, in establishing clinical remission, defined as CDAI < 150, at Week 10
- To evaluate the impact of filgotinib, when compared to placebo, on change in CDAI scores
- To evaluate the safety and tolerability of filgotinib

CCI

[REDACTED]

[REDACTED]

[REDACTED]

[REDACTED]

### **3. STUDY DESIGN**

#### **3.1. Endpoints**

The primary endpoint of this study is:

- Proportion of subjects achieving clinical remission, defined as CDAI < 150, at Week 24

The secondary endpoints of this study are:

[figure not shown]
- Change from baseline in terminal ileum segmental MaRIA score at Week 24
- Change from baseline in distal ileum segmental MaRIA score at Week 24
- Change from baseline in jejunum segmental MaRIA score at Week 24
- Proportion of subjects achieving MaRIA remission in terminal ileum segment at Week 24
- Proportion of subjects achieving MaRIA remission in distal ileum segment at Week 24
- Proportion of subjects achieving MaRIA remission in jejunum segment at Week 24
- Proportion of subjects achieving MaRIA response in terminal ileum segment at Week 24
- Proportion of subjects achieving MaRIA response in distal ileum segment at Week 24
- Proportion of subjects achieving MaRIA response in jejunum segment at Week 24
- Proportion of subjects achieving subject level small bowel MaRIA remission at Week 24
- Proportion of subjects achieving subject level small bowel MaRIA response at Week 24
- Proportion of subjects achieving early clinical remission by CDAI at Week 10
- Change from baseline in CDAI scores at Week 10
- Change from baseline in CDAI scores at Week 24

CCI

**Figure 3-1. Study Design Schematic**

FIL filgotinib; PBO placebo; mg milligram.

\* Non responders are subjects who never achieved a  $\geq 70$  point CDAI reduction from baseline or CDAI  $< 150$  at any point up to and including Week 10

\*\* Disease worsening is defined as a  $\geq 100$  point increase in CDAI score from the Week 10 value and CDAI score  $\geq 220$  points at 2 consecutive visits

CCI

### This study includes:

- Screening (Days -30 to -1)
- Randomization (Day 1)
- Blinded Treatment Period (Day 1 to Week 24)

Efficacy assessment: At Week 24, CDAI score to assess clinical remission; MRE to assess radiographic changes

CCI [REDACTED]  
CCI [REDACTED]

- Post-Treatment (PTx) safety assessments

Three horizontal bars representing CCI values for three different categories. The first bar is black and spans from approximately 10 to 40. The second bar is black and spans from approximately 10 to 90. The third bar is black and spans from approximately 10 to 90.

### 3.3. Study Treatments

Subjects who meet protocol eligibility criteria will be randomized in a blinded fashion in a 2:2:1 ratio to 1 of 3 treatment groups as follows:

**Treatment group 1 (n = 40):** Filgotinib 200 mg and PTM filgotinib 100 mg, once daily

**Treatment group 2 (n = 40):** Filgotinib 100 mg and PTM filgotinib 200 mg, once daily

**Treatment group 3 (n = 20):** PTM filgotinib 200 mg and PTM filgotinib 100 mg, once daily

Note: US males who have not failed at least 2 biologic therapies (any TNF $\alpha$  antagonist and vedolizumab) will be randomized in a 2:1 ratio to either filgotinib 100 mg or matching placebo.

Treatment assignments will be stratified according to the following factors:

- Concomitant use of oral, systemically absorbed corticosteroids (eg, prednisone) at Day 1, (Yes or No)
- Concomitant use of immunomodulators (eg, 6-MP, azathioprine, MTX) at Day 1, (Yes or No)
- Prior exposure to biologics (eg, TNF $\alpha$  antagonists or vedolizumab), (Yes or No)

#### **3.4. Duration of Treatment**

Randomized subjects will receive a maximum of 24 weeks of study drug. Subjects who are non-responders based on the results of the Week 10 assessments (see Section 3.6) or who meet disease worsening criteria after Week 10 (see Section 3.7) must be discontinued from blinded treatment (see Section 3.5.2).

#### **3.5. Criteria for Study Drug Interruption or Discontinuation**

##### **3.5.1. Study Drug Interruption Considerations**

The Gilead Medical Monitor should be consulted prior to study drug interruption when medically feasible.

Study drug interruption should be considered in the following circumstances; *prior to resumption of study drug, the investigator should discuss the case with the Gilead Medical Monitor:*

- Intercurrent illness that would, in the judgment of the investigator, affect assessments of clinical status to a significant degree
- Subject is scheduled for elective or emergency surgery (excluding minor skin procedures under local or no anesthesia); timing of study drug pausing should be determined in consultation with the Gilead Medical Monitor
- Any subject who develops a new infection during the study should undergo prompt and complete diagnostic testing appropriate for an immunocompromised individual, and the subject should be closely monitored

*NOTE: During the time of study drug interruption for any of the above, the subject may continue to have study visits and to take part in procedures and assessments, if deemed medically appropriate by the investigator.*

### **3.5.2. Study Drug Discontinuation Considerations**

The Gilead Medical Monitor should be consulted prior to study drug discontinuation when medically feasible.

Study drug must be permanently discontinued in the following instances:

- Any opportunistic infection
- Any **serious** infection that requires antimicrobial therapy or hospitalization, or any infection that meets SAE reporting criteria.
- Febrile neutropenia (temperature  $> 38.3^{\circ}\text{C}$  or a sustained temperature of  $> 38^{\circ}\text{C}$  for more than one hour) with absolute neutrophil count of  $< 1,000/\text{mm}^3$
- Symptomatic anemia (eg, signs/symptoms including pallor, shortness of breath, new heart murmur, palpitations, lethargy, fatigue) with hemoglobin  $< 7.5\text{ g/dL}$ , or if transfusion is indicated regardless of hemoglobin value
- Complicated herpes zoster infection (with multi-dermatomal, disseminated, ophthalmic, or CNS involvement)
- Evidence of active Hepatitis C Virus (HCV) during the study, as evidenced by HCV RNA positivity
- Evidence of active Hepatitis B Virus (HBV) during the study, as evidenced by HBV DNA positivity
- Any thromboembolic event that meets SAE reporting criteria
- Unacceptable toxicity, or toxicity that, in the judgment of the investigator, compromises the subject's ability to continue study-specific procedures or is considered to not be in the subject's best interest
- Subject request to discontinue for any reason
- Subject noncompliance
- Pregnancy during the study; refer to Section [7.7.2.1](#)
- Discontinuation of the study at the request of Gilead, a regulatory agency or an institutional review board or independent ethics committee (IRB/IEC)
- Subject use of prohibited concurrent therapy *may* trigger study drug discontinuation; consultation should be made with the Gilead Medical Monitor.

- **Laboratory Criteria:** After becoming aware of any of the below described abnormal laboratory changes occurring at any one time, an unscheduled visit (ie, sequential visit) should occur to retest within 3 to 7 days (except creatinine, which should be retested 7 to 14 days apart).

Two sequential neutrophil counts < 750 neutrophils/mm^3 (SI: < 0.75 x10^9 cells/L)

Two sequential (3 to 5 days apart) platelet counts  
< 75,000 platelets/mm^3 (SI: < 75.0 x10^9 cells/L)

2 sequential aspartate aminotransferase (AST) or alanine aminotransferase (ALT) elevations > 3x the upper limit of normal (ULN) and at least one of the following confirmed values:

- total bilirubin >2x ULN
- INR > 1.5
- or accompanied by symptoms consistent with hepatic injury

For any subject with an **initial** AST or ALT elevation > 3x the ULN, at the time of the **second confirmatory draw**, an INR, prothrombin time (PT) and partial thromboplastin time (PTT) must also be drawn

Two sequential AST or ALT > 5 x ULN

Two sequential values for estimated creatinine clearance (CLcr) < 35 mL/min based on the Cockcroft-Gault (CC&G) formula

$$\text{Male: } \frac{(140 - \text{age in years}) \times (\text{wt in kg})}{72 \times (\text{serum creatinine in mg/dL})} \text{ CL}_{\text{cr}} \text{ (mL/min)}$$

$$\text{Female: } \frac{(140 - \text{age in years}) \times (\text{wt in kg}) \times 0.85}{72 \times (\text{serum creatinine in mg/dL})} \text{ CL}_{\text{cr}} \text{ (mL/min)}$$

Subjects are free to withdraw from the study at any time without providing reason(s) for withdrawal and without prejudice to further treatment. The reason(s) for withdrawal will be documented in the electronic case report form (eCRF).

Subjects who permanently discontinue study drug for any reason should discuss their continued care plan with their physician.

Subjects who permanently discontinue study drug for pregnancy should not continue in the study; if there are any questions regarding permanent discontinuation, these should be discussed with the Sponsor.

Subjects withdrawing from the study should complete Early Termination (ET), followed by PTx assessments 30 days after the last dose of study drug.

Reasonable efforts will be made to contact subjects who are lost to follow-up. All contacts and contact attempts must be documented in the subject's file.

The Sponsor has the right to terminate the study at any time in case of safety concerns or if special circumstances concerning the study medication or the company itself occur, making further treatment of subjects impossible. In this event, the investigator(s) and relevant authorities will be informed of the reason for study termination.

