#### 6.7.1.2. Laboratory Re-tests

A single retest of screening labs is permitted only if there is reason to believe the retest value will be within accepted parameters, or if the initial value was either due to a sample processing error or due to an extenuating circumstance.

Subjects meeting all of the inclusion criteria and none of the exclusion criteria will return to the clinic within 30 days after screening for randomization into the study. Subjects may be randomized more than 30 days after initial screening if they receive permission from the Gilead Medical Monitor. If the subject does not begin the treatment within this 30-day window, specific screening evaluation procedures may need to be repeated at the direction of the Gilead Medical Monitor. No more than 1 repeat screening visit is allowed for each subject, unless prior written approval has been provided by the Sponsor.

Laboratory values outside the normal range will be flagged and clinical relevance will be assessed by the investigator. More frequent sampling as well as additional tests may be performed as deemed necessary by the investigator.

Note that in the case where clinically significant laboratory test results are a potential reason for discontinuation from the study drug and/or withdrawal from the study, retesting of the affected parameter(s) should be prompt (within 3 to 7 days [except creatinine, which should be retested 7 to 14 days apart]).

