## **7.6.           Toxicity Management**

All clinical and clinically significant laboratory toxicities will be managed according to uniform guidelines detailed in [Appendix 3](#), and as outlined below.

Refer to Section [3.5](#), Criteria for Study Drug Interruption or Discontinuation, for additional specific discontinuation criteria. Specific toxicity discontinuation criteria in Section [3.5](#) supersede the below general toxicity guidelines, and in general, where discrepancy is present, the more conservative criteria should apply. The Gilead Medical Monitor should be consulted prior to study drug discontinuation when medically feasible.

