### **7.6.1.       Grades 1 and 2 Laboratory Abnormality or Clinical Event**

Continue study drug at the discretion of the investigator.

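### Protocol 3.5.2 allows a platelet retest at 3 to 7 days, but its mandatory platelet stop counts only results 3 to 5 days apart, so a later confirmed low count can delay the stop or leave it to judgment.

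*Protocol*

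**What the plan says.** The laboratory criteria in Protocol 3.5.2 belong to the list of events after which study drug has to be stopped for good. Their lead-in says that, once the site is aware of a listed abnormality, an unscheduled visit "should occur to retest within 3 to 7 days (except creatinine, which should be retested 7 to 14 days apart". Section 6.7.1.2 (Laboratory Re-tests) gives the same rule for results that could lead to discontinuation: retesting "should be prompt (within 3 to 7 days [except creatinine, which should be retested 7 to 14 days apart". Neither sentence mentions platelets.

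The individual criteria follow the lead-in. The neutrophil line reads "Two sequential neutrophil counts < 750" and one liver line reads "Two sequential AST or ALT > 5 x ULN". Neither has an interval of its own, and nor do the combined AST/ALT criterion or the creatinine clearance criterion. The platelet line does: it requires "Two sequential (3 to 5 days apart) platelet counts" below 75,000/mm3.

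Other text can also lead to stopping. The 3.5.2 list has an item that opens "Unacceptable toxicity, or toxicity that, in the judgment of the investigator". Section 7.6 ranks Section 3.5 above the general toxicity guidelines and adds that "in general, where discrepancy is present, the more conservative criteria should apply". Section 7.6.1 covers Grades 1 and 2 with one instruction: "Continue study drug at the discretion of the investigator". Section 7.6.2 withholds drug for a related Grade 3 finding and stops it permanently only on related recurrence after re-challenge. Section 7.6.3 stops it for a confirmed, related, clinically significant Grade 4 finding, and sends treatment-emergent toxicities to a discussion with the Medical Monitor.

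**The concern.** A retest rule and the stop that depends on it should use the same interval. Here they do not. A site can retest platelets on a day that the lead-in and 6.7.1.2 both allow, confirm a count below 75,000/mm3, and still not meet the literal condition for the mandatory stop. A neutrophil or AST/ALT result confirmed on that same day would meet its condition.

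At stake is an automatic safety stop that applies whatever the cause of the low count. Where it does not apply, the decision falls to routes that depend on investigator judgment, grade, or an assessment of relatedness. Nothing in the protocol or SAP says how to treat a second low platelet count that falls outside the 3 to 5 day interval.

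**Working it through.** The plan gives no figure to reproduce. The check compares two sets of days.

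**Inputs**
- Permitted retest day r, counted from awareness: 3, 4, 5, 6 or 7 (3.5.2; the 3 to 7 day window is repeated in 6.7.1.2).
- Qualifying spacing between the two platelet counts: 3, 4 or 5 days (3.5.2).
- Lag L from first draw to awareness: not given in the documents, so it is an assumption and is shown over a range of 0 to 3 days.

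**Step 1: which permitted retest days qualify.** Spacing between draws = L + r. The stop is met when 3 ≤ L + r ≤ 5.

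| Assumed L (days) | Retest days that meet the stop | Retest days that miss it | Share missed |
|---|---|---|---|
| 0 | 3, 4, 5 | 6, 7 | 2 of 5 |
| 1 | 3, 4 | 5, 6, 7 | 3 of 5 |
| 2 | 3 | 4, 5, 6, 7 | 4 of 5 |
| 3 | none | 3, 4, 5, 6, 7 | 5 of 5 |

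Days 6 and 7 miss at any L ≥ 0, because L + r is then at least 6.

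**Step 2: what happens after a miss.** The second low count is itself a listed abnormality, so the lead-in calls for another retest. Take L = 0 and number days from the first draw. If the second count is on day 6, a third low count on days 9 to 11 (6 + 3 to 6 + 5) is 3 to 5 days after the second and triggers the stop. If the second is on day 7, the days are 10 to 12. The stop then comes 3 to 5 days after the second low count. If the third count is again 6 or 7 days later, the stop is missed again. If L is 3 or more at every retest, no retest made 3 to 7 days after awareness can qualify, so the stop would need an earlier extra draw, which 6.7.1.2 permits.

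**Step 3: scheduled draws.** Hematology is scheduled on study days 1, 15, 29, 43, 71, 99, 127 and 169, with windows of ±3, ±3, ±3, ±2, ±3, ±3 and ±5 days from Week 2 onward (Appendix 2). The smallest possible gaps are:
- Day 1 to Week 2: 12 − 1 = 11
- Week 2 to 4: 26 − 18 = 8
- Week 4 to 6: 40 − 32 = 8
- Week 6 to 10: 69 − 46 = 23
- Week 10 to 14: 96 − 73 = 23
- Week 14 to 18: 124 − 102 = 22
- Week 18 to 24: 164 − 130 = 34

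All exceed 5 days, so from Day 1 to Week 24 a qualifying pair needs an unscheduled draw.

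**Step 4: the proposed wording.** With a condition of at least 3 days apart, L + r ≥ 3 for every r from 3 to 7 and every L ≥ 0, so no permitted retest day is lost. Widening the interval to 3 to 7 days apart would not achieve this: with L = 1 and r = 7 the spacing is 8.

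**The case against.** The strongest reply is that the platelet line is the specific rule and governs platelets. A site that reads it so retests on days 3 to 5, and with no lag that meets both rules. On this view a day 6 or 7 retest is simply late, and platelets need no named exception because 3 to 5 days lies inside 3 to 7. This is a fair reading. It does not settle the matter: both statements of the retest rule name creatinine alone as an exception, and even on this reading the protocol does not say what follows a second low count that arrives late.

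The second reply is that the rule largely corrects itself, because a further retest is due after any low count. This stands and limits the consequence. A reader might infer that the mandatory stop is lost and that a subject with confirmed low platelets simply stays on drug. The documents do not support that. Another retest is called for, the toxicity goes to the Medical Monitor, and the unacceptable-toxicity item makes stopping mandatory once the investigator has made that judgment.

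The third reply is the tie-break in 7.6, which favours stopping. It is qualified as a general principle and appears where Section 3.5 is ranked against the general guidelines, so it does not clearly resolve a mismatch inside 3.5.2.

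Two limits apply. Section 7.6 refers to Appendix 3, whose content does not appear in the available text, so any further backstop there could not be checked. The toxicity grading scale is an external document, so the graded rule that would apply to a count below 75,000/mm3 is not established here.

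**Conclusion.** The mismatch is real, and it is minor. On the literal text, a confirmatory platelet count below 75,000/mm3 on day 6 or 7 does not trigger the mandatory stop, and with a lag between draw and awareness neither do some earlier days. The likely effect is a stop that waits for a further retest, or one that rests on investigator or Medical Monitor judgment.

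The figure of 2 in 5 assumes that both intervals start at the first draw, whereas the retest clock starts at awareness. A reader might take it as a 40% chance of a missed stop. It is not: it counts calendar days, and the documents say nothing about how retests are distributed over those days, how quickly results are returned, or how often platelets fall this low. Nor do the two rules make compliance impossible, since with no lag days 3 to 5 satisfy both. No efficacy endpoint or analysis uses this rule.

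**What to change.** In 3.5.2, replace the platelet interval with a minimum only: two sequential counts below 75,000/mm3 at least 3 days apart require permanent discontinuation. Any retest done under the 3 to 7 day rule that confirms the low count would then trigger the stop, whatever the lag.

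Keep the 3-day minimum. Removing the interval altogether would force permanent discontinuation on a next-day repeat, which the present rule does not do.

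If a faster platelet recheck is intended, name 3 to 5 days as the platelet retest target in both 3.5.2 and 6.7.1.2, and not as a condition of the stop.

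The cost is about one line in 3.5.2 and, if the target is kept, one in 6.7.1.2. Because it changes a mandatory safety criterion, it should be made by protocol amendment with documented IRB/IEC approval under 9.2.1. No SAP efficacy section needs to change.
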